5.2.5 Follow-up and Final Visits

Assessments given at baseline will be repeated three times over the following 24 months (approximately 6, 12, and 24 months*), plus the option of a phone assessment or a mailed questionnaire at 18 months.

*Participants who are unable to or decline to complete follow up in-person visits will be given the option to complete an abbreviated assessment by phone/mail. These participants will still be given the \$50 incentive.

All Follow-up Visits and 24-Month (Final) Visit

- ActiGraph (not at 6-month visit)
- Physical Function Tests
- Vital Signs
- Questionnaire packet
- Neuropsychological Test Battery*
- Adverse Events
- COVID/GAD-2 (if applicable**)
- Medication Questionnaire (24-month only)***

* Several integral tests in the Neuropsychological Test Battery could not be administered via telephone, so those were not collected post-March 2020, when Covid-19 interrupted the study.

**The COVID/GAD-2 Questionnaire may be administered at one or more follow-up time points, if applicable based on the prevalence of COVID in the community.

*** The medication questionnaire will be pilot tested at the 24-month timepoint in 10-15 participants. After study team debriefing for QA and additional

training/clarification, we will implement for all future visits.

The study team will notify all participants once their participation has ended at two years and when the overall study has ended. The team will mail a letter thanking each person for their participation. The letter will include a 1-page summary of study findings in lay language, a “graduation” certificate, and a reference to the first article resulting from the study.

The study does not plan to terminate anyone’s participation early. They will continue in the study if they develop dementia, for as long as they and their legally authorized representative are willing to continue. For people unable to attend follow-up evaluations, we will offer a phone follow-up (CASI, neuropsychological tests, survey questions, AEs). Possible reasons for early withdrawal include medical event, illness, too busy, etc. If a participant asks to withdraw, we will first ask them if we can contact them again in a few months. If they are unwilling, we will ask permission to follow via medical records only.

Exit Interview (Optional)

After completing the study, participants may be invited to complete an exit interview by phone about their experience with the program and any feedback they have. This will help us improve the program. Participation in the exit interview is optional; if they agree to participation, we will ask to audio-record and transcribe the interview, but audio-recording is also optional.

5.3 Outcomes

Primary Outcome: Two-year Cognitive Change (Composite Score): Cognitive function will be measured by a global composite score from the modified Neuropsychological Test Battery (mNTB), a comprehensive battery including tests of memory (WMS-R Logical Memory, Consortium to Establish a Registry for Alzheimer’s Disease [CERAD] Word List); attention (WMS-R Digit Span); executive functioning/processing speed (Trail Making Test, Stroop Test, WAIS-R Digit Symbol); and language [Category Fluency Test; Phonemic Fluency (FAS)].

Outcome measures in Alzheimer’s risk reduction trials need to be sensitive to detecting subtle cognitive changes. We selected the mNTB to meet this need based on several lines of evidence for its strength as an outcome measure. Specifically, the original NTB,(6) on which the mNTB builds, is well-validated with strong test-retest reliability,(6,7) ability to distinguish between individuals at different clinical stages (i.e., normal cognition, MCI, AD),(7) and sensitivity to detecting cognitive change in early stages of Alzheimer’s.(6)

Changes made to the protocol due to Covid-19, i.e., switching to telephone data collection, may limit our ability to examine cognitive change effectively, as several of the most important cognitive tests cannot be administered via telephone.

Secondary outcomes:

a) Improvement on Alzheimer's risk factors. Because this is a pilot study, one of our goals is to quantify the number and type of Alzheimer's risk factors each person has at baseline as well as change in each risk factor over two years in response to the SMARRT intervention. This will be accomplished using a combination of validated objective and self-report measures as well as EHR data. We chose to use individual measures rather than an AD risk score so that we could examine each risk factor independently. In addition, current AD risk scores do not include all of the risk factors being targeted in this study. Specific measures include:

- Self-reported physical activity (Rapid Assessment of Physical Activity for Older Adults (RAPA)): a validated 9-item self-report inventory assessing physical activity, which is designed for use with older adults and based on CDC recommendations for physical activity.
- Objectively measured physical activity (Actigraphy): participants will wear an ActiGraph wGT3X+ (Pensacola, FL) waist-worn accelerometer for 7 days prior to measurement visits at baseline, 12 months, and 24 months. Data from the ActiGraph will be aggregated using ActiLife software with counts over 1040 per minute used as the threshold for moderate or higher intensity activity (a cut point that appears to be valid for older adults).
- Leisure / Social Activity (PROMIS Satisfaction with Participation in Discretionary Social Activities): 12-item questionnaire which asks individuals to rate how satisfied they have been with their engagement with social and other leisure activities and social connectedness in the past 7 days on a 5-point Likert scale (not at all ... very much).
- Cognitive activity (Cognitive Activity Questionnaire): 11-item questionnaire which asks how often an individual engages in activities such as reading the newspaper, playing games (e.g., crosswords, puzzles), playing a musical instrument, and other cognitively stimulating hobbies/leisure activities on a 6-point Likert scale (once a month/never ... every day).
- Control of cardiovascular risk factors (hypertension, diabetes): Blood pressure and HbA1c values will be ascertained from the KPWA EHR. In addition, at each measurement visit, height, weight, and blood pressure will be assessed. Height and weight will be used to calculate body mass index (BMI).
- Smoking: Participants will be asked to self-report current tobacco usage, including questionnaire items: "Have you smoked even a puff in the last 7 days?" and if yes, "How many cigarettes have you smoked in the last 7 days?"
- Diet (MIND diet score): The Mediterranean-DASH Intervention for Neurodegenerative Delay (MIND) diet combines elements of the Mediterranean and the Dietary Approach to Systolic Hypertension (DASH) diets. The 15-item questionnaire assesses frequency of consumption of specific food types (e.g., green leafy vegetables, red meat) over the past 6 months.
- Depressive symptoms (Center for Epidemiologic Studies – Depression Scale, CES-D): 20-item questionnaire that assess both positive and negative affect over the last week rated on a scale from 0 (rarely or none of the time) to 4 (most or all of the time).

- Sleep quality (Pittsburgh Sleep Quality Index, PSQI): 19 item questionnaire that assesses sleep quality and disturbances over the past month (not at all, less than once a week, once or twice a week, three or more times a week).
- Potentially harmful medications (identified from KPWA pharmacy database): based on a detailed list of contraindicated medications developed for the intervention (see Intervention section). Additionally, a medication questionnaire will assess the use of over-the-counter [OTC] medications containing ingredients that increase risk of cognitive impairment/dementia.
- The onset of Covid-19 may affect the ability of participants to achieve risk factor reduction. In an exploratory outcome we will examine the effect of the Covid-19 pandemic on risk factors.

b) Individual cognitive domain scores

c) Physical performance (Short Physical Performance Battery, SPPB): The SPPB was developed by the National Institute on Aging (NIA) to provide an objective tool for measuring physical performance in older adults. Each component is individually scored on a scale of 1-4 (balance, lower extremity strength/chair stands, and gait speed/time to walk 4 meters) according to SPPB scoring protocols. The total SPPB score is the sum of the 3 component scores and ranges from 0 to 12. We will also examine scores on subscales (time to complete 5 chair stands, time to walk 4 meters). [Because this requires in-person observation, we have very few timepoints with this data due to Covid-19.]

d) Functional ability (Cognitive Function Instrument, CFI): 14-item self-report inventory of cognitive and functional difficulties in everyday tasks (e.g., remembering appointments, managing finances, driving). Total scores range from 0 to 14, with higher scores indicating greater difficulty in everyday tasks.

e) Quality of life (PROMIS Global Health): 10-item self-report inventory which asks individuals to rate their quality of life including in terms of their overall physical and emotional health.

f) Incidence of MCI and Alzheimer's disease: While the incidence of clinically significant cognitive impairment is anticipated to be low, we will hold consensus conferences to identify MCI and dementia including Alzheimer's in people who meet one of the following criteria: 1) Full-length CASI score < 86 (or < 27 on the abbreviated telephone CASI for those unable to complete in-person) or 2) assessors observe or ascertain a noticeable decline in function. For these individuals, we will follow standard guidelines developed and used since 1994 in the ACT study to determine cognitive status using DSM-IV criteria for determination of the presence and diagnostic subtype of dementia. The diagnosis of Alzheimer's disease will be based on type of dementia according to current NINCDS-ADRDA diagnostic criteria for Alzheimer's and other types of dementia. We will define MCI broadly based on the Petersen criteria for MCI. We will further define MCI based on cognitive domain of deficit in order to yield categories of amnestic MCI, single non-memory impairment MCI and multiple domain MCI.

6 STUDY INTERVENTIONS

6.1 Interventions, Administration, and Duration

SMARRT Intervention Arm

After baseline assessments have been completed, the intervention team (including a nurse care manager and a behavioral interventionist) will use a standardized procedure to develop an individualized Alzheimer's Risk Profile for each patient randomized to the SMARRT intervention arm. This will include a graphic display of the targeted risk factors showing areas where the participant is doing well (green), areas where they can continue to improve (orange), and areas that are of particular risk for them (red). Patients will then meet in-person with an interventionist to review their risk profile and develop a personalized risk reduction action plan. Interventionists will elicit participants' values and motivators to reduce Alzheimer's risk and will use a decisional balance process informed by motivational interviewing and confidence ratings to help them choose 1-3 specific, achievable risk reduction steps that they are most ready to adopt. Participants will be provided with tools to track their progress. At each subsequent visit, interventionists will review progress, problem-solve barriers, and set new goals as needed. Targeted areas will include: increasing physical, mental and social activities; quitting smoking; healthy diet; controlling cardiovascular risk factors (diabetes, hypertension); reducing depressive symptoms; improving sleep; and decreasing use of potentially harmful medications. Following detailed protocols, the intervention team will provide counseling if participants experience distress related to being informed of their Alzheimer's risk.

Interventionists will provide participants with a menu of options for each targeted risk factor, and goals will be individualized to preferences, barriers, and motivators up front to optimize intervention adherence (see Table below). For each target, there are options that leverage technology as appropriate for the participants' interest and skill level. Non-technology-based options are provided for each target as well.

For management of medical conditions (e.g., hypertension, diabetes, depression, sleep disorders), a "treat-to-target" approach will be used. This will involve setting discrete goals for targeted conditions (e.g., blood pressure, HbA1c, depressive symptoms) in consultation with the primary care team, systematically monitoring patient progress, adjusting treatment as needed (treat-to-target) and supporting patient self-care. Each week, the intervention team will meet with the clinical support team (MDs and clinical psychologists) for case reviews. Treatment algorithms will be based on standard KPWA treatment recommendations synthesized from national guidelines. Approval to exercise will be obtained from primary care physicians (PCPs) to ensure participants can safely engage in exercise prior to receiving interventions. Those who are approved and interested will be encouraged to gradually increase their physical activity levels, focusing on walking. In addition, our protocol includes strategies to reduce sitting behavior as an alternative in those who are not interested or able to increase physical activity levels. The SMARRT study physician or nurse will make recommendations to the participant and their PCP about management of targeted medical conditions and use of specific high-risk medications via Epic messaging, a secure, electronic, internal messaging system that enables clinical staff to communicate with each other about patient care. A detailed list of contraindicated

medications including generic and brand names was developed using the 2015 updated Beers criteria for potentially inappropriate medications in older adults and a Kaiser reference for high-risk medications in the elderly, focusing on medications that impact cognitive function. Examples of targeted medications include those with strong anticholinergic properties, such as some antihistamines (e.g., diphenhydramine), some antidepressants (e.g., amitriptyline, paroxetine), and sedative-hypnotics (e.g., alprazolam, lorazepam). Nurses will work collaboratively with the primary care team to deprescribe contraindicated medications, and health coaches will work with participants on behavioral approaches to manage underlying conditions such as depression or insomnia.

Interventionists will follow a standard protocol for delivering the SMARRT intervention that allows for personalization of the specific risk reduction action plan; these plans will evolve over time according to participant progress, motivation and preferences or newly identified risk factors. Staff will use a tracking database to record information for each participant, including date and time of session, identified risk factors, motivational barriers and important values, and the outcome of discussions around developing goals. For each participant, the exact number and mode (phone or in-person) of contacts will differ, but we will aim to have at least 1 contact per month with each participant. Best practice will include in-person meetings twice a year during the 2-year intervention period. Even if a participant has relatively fewer risk factors, or successfully addresses all of their risk factors, interventionists will continue to check in with them to ensure that they are maintaining their healthy behaviors over time.

Table. Targeted Risk Factors and Approaches and Outcomes in SMARRT

Risk Factor	Goal	Menu of Options Tailored to Individual Preferences & Abilities	Outcome Measures
Poorly controlled hypertension	<140/90 (<130/90 in patients with 10-year atherosclerotic cardiovascular disease risk \geq 10%)	Exercise, diet, medication changes using stepped care “treat to target” approach with primary care provider (PCP)	Blood pressure (study visits; EHR)
Poorly controlled diabetes	HbA1c between 7 and 8	Exercise, diet, medication changes using stepped care “treat to target” approach with primary care	HbA1c (EHR)
Physical inactivity	Increase by 2500 steps per day or maintain if they are over 10,000 steps/day, or work up to 8,000 steps per day	KPWA covered programs (e.g., Silver Sneakers, EnhanceFitness), community programs (e.g., YMCA, mall walking), smart phone apps (e.g., Apple Health, MyFitnessPal, MapMyWalk), wearable devices (e.g., pedometer, Fitbit), protocol to reduce sitting	Rapid Assessment of Physical Activity (RAPA) for Older Adults; Actigraphy
Lack of mental stimulation	Increase engagement in cognitively stimulating activities that are enjoyable	Senior center activities, local college classes, crossword puzzles and games, cognitive training web programs, smart phone apps (e.g., Lumosity, Brain HQ), on-line classes, volunteering; mindfulness	Cognitive Activities Questionnaire
Social isolation	Increase social engagement	Senior center activities, group exercise, social networking websites (e.g., Facebook), video chat tools, volunteering	PROMIS – Satisfaction with Participation in Discretionary Social Activities
Depressive symptoms	Fewer depressive symptoms	Behavioral activation, referral to behavioral health for CBT, antidepressant medication via PCP, smart phone apps based on CBT (e.g., MoodKit) or mindfulness (e.g., Mindfulness Coach)	Center for Epidemiologic Studies – Depression Scale
Sleep difficulty	Improvement on self-reported sleep quality and	Sleep hygiene and sleep restriction education, CBT for Insomnia (CBT-I), smartphone apps (e.g. Sleepio),	Pittsburgh Sleep Quality Index

	sleep duration	physical activity, behavioral activation	
Smoking	Reduction/cessation	Referral to Quit for Life, comprehensive program at no cost to KPWA members delivered by phone, web, and/or smart phone app; mobile tools (NCI QuitPal)	Self-reported current tobacco usage
Unhealthy diet	Increase adherence to MIND diet	Education about neuroprotective foods, self-monitoring neuroprotective food intake with paper food logs or websites/apps (e.g. Fitbit, MyFitnessPal, MyPlate)	Mediterranean-DASH Intervention for Neurodegenerative Delay (MIND) Diet Score
Contraindicated medications	Elimination/minimization	Education on alternatives, including nonpharmacologic therapy	Contra-indicated medications for cognition (2015 Beers criteria and KPWA list)

Health Education Control Arm

In this pragmatic pilot trial, our goal is to compare the personalized SMARRT intervention to what is currently ‘usual care’ in the healthcare system, while also providing enough interaction to maintain retention and blinding. Therefore, participants randomized to the Health Education (HE) group will receive mailed materials (typically 1-2 pages) every 3 months: general information on Alzheimer’s and dementia risk reduction using materials from sources such as the Alzheimer’s Association and educational materials commonly provided as part of routine care at KPWA. The general information provided will address factors that will be targeted in the SMARRT intervention, including physical, mental and social engagement; management of cardiovascular risk factors; quitting smoking, healthy diet; depression; sleep; and contraindicated medications. HE participants will not be provided with personalized information about their Alzheimer’s and dementia risk.

Included in the mailings every 3 months will be a form asking if the HE participant has experienced a serious adverse event in the prior 3 months, and if so, a description, date(s), whether the participant has recovered, treatment plan if any, and whether we can call the participant later to see how they are doing. This approach will allow for more standardized, routine collection of SAEs among the control group.

We may contact the primary care providers of Health Education program participants, for example if the blood pressure results or cognitive test results at a measurement visit are outside of the expected range.

6.2 Handling of Study Interventions

Interventionists will follow a standard protocol for delivering the SMARRT intervention that allows for personalization of the specific action plan. Staff will use a tracking database to record information for each participant, including date and time of session, identified risk factors, motivational barriers and important values, and the outcome of discussions around developing goals. Also documented in the tracking database will be notes about participants’ follow-through on recommendations and weekly case review recommendations with the clinical support team to supply information about intervention adherence.

6.3 Concomitant Interventions

6.3.1 Allowed Interventions

Unless specifically targeted for intervention, participants will remain on medication and dosages as prescribed by their primary care provider.

6.3.2 Prohibited Interventions

As dementia at baseline is an exclusionary disorder, dementia medications at baseline (such as donepezil or memantine) will be prohibited. These medications will be allowed

if they are newly prescribed during the 24-month follow-up period.

6.4 Adherence Assessment

Interventionists will use the tracking database to carefully document each contact with participants, including the type (in person, phone) and outcome (risk factor targeted, goal, whether the goal was met, comments). This will enable us to determine the total number and type of contacts per participant, the number and types of risk factors targeted, and the extent to which goals were achieved. Interventionists also will document weekly case review recommendations with the clinical support team to supply information about intervention adherence. In the control arm, there is no active intervention (only passive materials, usual care) so we cannot assess adherence or engagement.

7 SAFETY ASSESSMENTS

7.1 Adverse Events and Serious Adverse Events

An adverse event (AE) is defined as a not serious condition (e.g., muscle aches from physical activity, abnormal lab values) that occurs during the study.

A serious adverse event (SAE) is defined as a serious (defined as death, life-threatening event, hospitalization, or significant disability) or unexpected (defined as new or more severe than expected) and possibly, probably or definitely study-related (e.g., occur during or shortly after study-related activities) condition occurring during the study period.

We expect AEs associated with this intervention to be minimal and consistent with daily risks (e.g., anxiety caused by assessments, muscle aches from physical activity); AEs will be tracked in the study database. AEs may be detected through reports or contact with study participants, from survey data, and from data in the EHR. All participants will be prompted to report AEs and SAEs at their measurement visits (approximately 6, 12, and 24 months). All participants will be asked to respond to an SAE form sent in the mail every three months (approximately months 3, 9, 15, and 21) when new health education materials are sent. Those in the SMARRT group may also report AEs during check-ins with their health coach. SAEs will be reported immediately to the project PIs and to the IRB and DSMB as described below.

Any activities that result in participant distress or serious physical activity-induced injury will be reported to the project PIs. The PIs will discuss all such events with co-investigators and the IRB and take other action(s) as appropriate (e.g., providing information about relevant community services to distressed participant). Summary reports of any such adverse events and subsequent actions taken will also be provided to the DSMB and NIA.

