7.2 Reporting Procedures

Serious Adverse Events (SAEs): SAEs will be reported to NIA and the Data and Safety Monitoring Board (DSMB) members by the PIs or their designees by email within 24 hours of learning of deaths, and 48 hours of learning of non-deaths. Official reports will be

submitted within five business days. The DSMB will request additional information as needed and will determine whether changes to the study protocol are warranted.

Adverse Events (AEs): AEs will be reported to NIA and the DSMB in aggregate form prior to the biannual DSMB meetings.

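### The SAE definition in section 7.1 leaves its or/and ungrouped: on either reading it overlaps the AE definition, and on one reading serious unrelated events have no category

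*Combined protocol and SAP*

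**What the plan says.** Section 7.1 gives the two definitions.

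- **AE:** "An adverse event (AE) is defined as a not serious condition (e.g., muscle aches from physical activity, abnormal lab values) that occurs during the study". It sets no condition on relatedness or expectedness.
- **SAE:** "A serious adverse event (SAE) is defined as a serious (defined as death, life-threatening event, hospitalization, or significant disability"), followed directly by "or unexpected (defined as new or more severe than expected) and possibly, probably or definitely study-related". The only guide to relatedness is an example in brackets, which refers to events during or soon after study activities. Nothing shows how the 'or' and the 'and' are grouped.

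Section 7.2 makes the label decide the reporting route. SAEs go to NIA and the DSMB "by email within 24 hours of learning of deaths, and 48 hours of learning of non-deaths", with an official report within five business days. For the rest, "AEs will be reported to NIA and the DSMB in aggregate form prior to the biannual DSMB meetings".

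No other section gives a second definition or a category for serious events judged unrelated.

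**The concern.** Every event should fall in exactly one category, because the category decides how quickly, and in what form, the DSMB hears of it. The wording of 7.1 does not achieve this.

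Two things are at stake, and they differ in weight. The overlap makes reporting inconsistent: the same minor event may be expedited by one member of staff and put in the aggregate report by another. The possible gap matters more. If staff treat relatedness as a condition for every SAE, a death or hospitalisation judged unrelated would have no defined route.

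Such a condition would also work unevenly between the arms, because relatedness is illustrated by timing around study activities. Section 6.1 aims for at least one interventionist contact a month in SMARRT, about 24 over two years (24 × 1), along with exercise advice, treat-to-target adjustment and deprescribing. HE participants receive mailed materials every three months, about 8 mailings (24 / 3), and section 6.4 describes that arm as having no active intervention. SAE counts filtered by relatedness would therefore not be a fair comparison of arms. Section 9.3 plans no interim analysis unless the DSMB asks for one on safety grounds, so the board depends on what reaches it.

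**Working it through.** The plan gives no figure to reproduce. The check is a complete enumeration of the definitions.

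**Inputs, all from section 7.1.** Let S = serious, U = unexpected, R = possibly, probably or definitely related.

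- AE = not S
- SAE, Reading A = (S or U) and R
- SAE, Reading B = S or (U and R)

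**All 2 × 2 × 2 = 8 combinations:**

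| S | U | R | Reading A | Reading B |
|---|---|---|---|---|
| yes | yes | yes | SAE | SAE |
| yes | yes | no | **neither** | SAE |
| yes | no | yes | SAE | SAE |
| yes | no | no | **neither** | SAE |
| no | yes | yes | **both** | **both** |
| no | yes | no | AE | AE |
| no | no | yes | AE | AE |
| no | no | no | AE | AE |

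**Counts.**

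- Reading A: 5 combinations in exactly one category, 1 in both, 2 in neither (5 + 1 + 2 = 8).
- Reading B: 7 in exactly one category, 1 in both, 0 in neither (7 + 1 + 0 = 8).

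**Consequence under section 7.2.** The 'both' row is not a death, so its SAE label starts the 48-hour clock while its AE label sends it to the aggregate report. The 'neither' rows have no route under 7.2.

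**Which reading does the rest of the protocol support?**

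- Section 6.1 sends HE participants "a form asking if the HE participant has experienced a serious adverse event in the prior 3 months". Its listed contents (description, dates, recovery, treatment plan, permission to call) include no relatedness item. Section 7.1 sends an SAE form to all participants.
- Section 7.2 starts the clock for deaths without any relatedness qualifier.
- Section 7.3 provides for triage and follow-up of SAEs, also without a relatedness condition.

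These passages fit Reading B better. None states it: each concerns how SAEs are collected, timed or followed, and none says which events count as SAEs.

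**The case against.** The strongest reply is that the harmful reading is the less natural one. Routine SAE collection in an arm that receives only mailed materials makes little sense if relatedness is required, and 7.2 and 7.3 refer to deaths and SAEs without that condition. Under Reading B no serious event is lost. What remains is over-reporting of minor events, which is a burden but errs towards safety. Section 7.1 also sends participant distress and serious injury from physical activity to the principal investigators and the IRB, with summaries to the DSMB and NIA, whatever label the event carries. The Manual of Procedures, which is not among the documents, may settle the matter.

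Most of this stands. It makes the gap conditional and answers part of the concern about exercise. It does not cover serious events linked to deprescribing or treat-to-target changes, it does not remove the overlap, and a protocol definition should not depend on inference from other sections.

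A reader might infer more than the documents support in three ways:

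- **That the plan does exclude unrelated deaths and hospitalisations.** This follows only under Reading A, and the context leans the other way.
- **That relatedness is judged before reporting by staff who know the arm.** No section says who judges it, when, or with what knowledge of allocation. Section 7.3 gives AE follow-up to health coaches in SMARRT and to the study nurse in HE, but follow-up is not causality assessment.
- **That most serious events in this age group would be lost.** The documents give no event rate and no share judged unrelated.

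**Conclusion.** The point holds as a defect of wording with a conditional safety consequence.

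- **Certain, on either reading:** 1 of 8 combinations (non-serious, unexpected, related) is both AE and SAE and falls under two incompatible reporting routes.
- **Conditional on relatedness governing serious events:** 2 of 8 combinations (serious and unrelated) are neither AE nor SAE, have no route in 7.2, and SAE capture would differ by arm.

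These are counts of combinations, not of events or probabilities; the number of participants affected cannot be derived from the documents. The conclusion rests on the text of 7.1 and 7.2 alone and assumes that the Manual of Procedures does not override it. Nothing shows that any event has been misclassified. The change should be made because it is cheap and concerns expedited safety reporting.

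**What to change.** Amend section 7.1 and align section 7.2 and the Manual of Procedures with it:

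1. Define an SAE as any event meeting one of the listed seriousness criteria, whatever its relatedness or expectedness, in both arms.
2. Record relatedness and expectedness as separate fields that do not decide whether an event is an SAE.
3. Report non-serious, unexpected, related events under their own heading, and state in 7.2 which reporting route applies to them.
4. Reconcile 7.1 with 7.2 so that every event has exactly one category and one route.
5. Check whether any logged serious event was left out of SAE reporting because it was judged unrelated. This is a check, not a presumption of error.

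The cost is one wording amendment to the protocol and Manual of Procedures, and possibly more expedited reports if relatedness has been used as a condition so far. Treatment, visits and sample size do not change.
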